3 OBJECTIVES

3.1 Study Objectives

The primary objective of this study is to assess the effects of the proposed behavioral intervention on tobacco abstinence and utilization of professional dental services.

The secondary objectives of this study include:

- Assess the impacts of the enhanced intervention on key secondary behavioral outcomes and select intermediate outcomes/process measures that could mediate treatment effects.
- Determine the effectiveness of the proposed enhanced intervention, whether it warrants dissemination to smokers through tobacco quitline programs nationally in the current form, or whether further refinement and evaluation are warranted.
- Calculate the incremental cost of adding the Oral Health 4 Life program to usual quitline care and create a decision support tool that quitline sponsors (i.e., potential purchasers of the program) can use to inform decisions about whether to offer the program.

The results of this project will inform whether the proposed intervention warrants further evaluation or dissemination through tobacco quitlines based on its effectiveness and help purchasers make informed decisions about providing the program.

The intervention will be offered to people seeking treatment for smoking cessation through one of the participating state-funded tobacco quitlines and will reach a high-need, lower-income population who are eligible for these free services.

Additional detail on the proposed enhanced intervention is included in sections 6 and 7.

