12.2 Sample Size Considerations

This is the first study to examine whether an integrated oral health promotion-smoking cessation program delivered through tobacco quitlines will increase abstinence rates, so the potential effect size of the intervention is unknown.

Given this, we have powered the study to detect a 9% increase in abstinence rates between the UC (12%) and enhanced intervention (21%) at 6 months. A difference of

this magnitude (nearly a two-fold increase) would be considered clinically meaningful, but is even more significant when viewed in terms of public health impact (defined as reach x effectiveness)⁴⁶ when the potential reach could be hundreds of thousands of smokers annually. Smaller effects could be statistically significant, but an effect of this size would be an unambiguous indicator that the intervention warrants dissemination. The UC cessation base-rate (12%) is estimated based on the actual end of treatment (~6 months) intent to treat 7-day PPA rates observed in the target quitlines (range =

Table 2. Power Calculations

	Effect Sizes		Sample Size
	Control	Intervention	
Abstinence	12%	20%	880
	12%	21%	712
	12%	22%	590
Dental care	5%	11%	856
	5%	12%	664
	5%	15%	376

All power calculations assume 90% power and use a normal approximation approach with pooled variance.

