11% - 12.5%) and is consistent with the estimated abstinence rate of tobacco quitlines based on a meta-analysis of the literature (average cessation rate at 6 months = 12.7% (95% CI, 11.3-14.2)).²³ With a sample of ~712 people, we will have 90% power to detect an 9% difference in rates of smoking abstinence at 6 months assuming a two-sided alpha-level=0.05 Wald Z test statistic for a difference between proportions using a normal approximation with pooled variance⁴⁷ and UC rate of 12%. This sample is also more than sufficient to detect a meaningful difference in the proportion of people who receive dental care (see Table 1). Although no participants will have seen a dentist in the past 6 months at enrollment as a condition of eligibility, it is possible a few will spontaneously seek dental care. Thus, we assume a base rate of 5% for this outcome in the UC group at 6 months. With the proposed sample, we will have >90% power to detect a 10% difference in dental care utilization between groups (e.g., 5% vs. 15%) and greater power to detect larger increases in treatment utilization. Increasing treatment utilization by 10% or more in this high risk population also has public health significance given the potential reach of the program. Each sample size estimate is based on complete case follow-up which will occur by design for all primary outcome analyses since we will be imputing missing values for the primary outcomes (missing cases will be assumed to be smokers and to not have visited the dentist). All analyses assume an intent to treat analysis with all subjects included as randomized. With a sample of n = 718, we also have 80% power to detect a difference of 7.6% in smoking abstinence and 5.6% in dental care utilization.

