Mediation Analyses. If the enhanced UC is more effective than UC for either primary outcome at 6 months, we will then conduct mediator analyses to assess whether relevant secondary outcomes measured at 2 months (self-efficacy, motivation, knowledge,) mediate at least part of this effect. Mediation will be explored separately for each significant main outcome. These analyses will be conducted using the framework recommended by Baron and Kenny,⁴⁹ but using more recent statistical methods developed to better quantify and decompose different aspects of the mediation effect.⁵⁰ Having demonstrated the association between the intervention and the outcome variable (the “total effect” of the intervention on the outcome), the second step will be to demonstrate the association between the intervention and each mediator. We will construct a regression model for each mediator with the 2 month score of the mediator as the dependent variable and intervention indicator as independent variables. We will conduct this for each potential mediator and only include those mediators that have at least a $P < 0.10$ -level significant relationship with the intervention as potential mediators in the following step. The third step is to demonstrate the reduction of the intervention effect on the outcome after removing the effect of the mediator(s). We will construct a multi-mediator inverse probability weighted (IPW) regression model. This approach allows us to estimate the direct effect of intervention after rebalancing the intervention groups with respect to the mediators. The application of the IPW approach, as compared to the traditional approach of adjusting for multiple mediators, allows us to more appropriately account for confounding between a mediator and the outcome both

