by additional mediators and by other measured variables. Further, we are better able to estimate the indirect effects of each mediator in a causal framework through decomposition of the total effect of intervention into indirect effects through each mediator and the direct effect after accounting for all mediators. Specifically, we will first model the probability of the intervention given the mediators (all mediators that were found associated with intervention in step 2) using logistic regression adjusting for potential baseline confounders. From this model we will obtain the estimated probabilities that each person received their observed intervention given their observed mediator value. We will then use an IPW regression to model the primary outcomes on intervention status while adjusting for the baseline level of the outcome and mediator and weighting out the effect of the mediator. Comparing the weighted to the unweighted model will allow us to estimate how much of the direct effect of intervention on the outcome can be explained by each potential mediator. We will further be able to quantify the amount of effect explained by each mediator independent of the other mediators.

Process Analyses. Summary statistics will be used to characterize quantitative acceptability ratings and scores. T-tests will be used to compare groups' on continuous ratings and chi-squares for proportions. Open-ended qualitative responses will be reviewed by investigators and may be transcribed and coded thematically, as needed to provide insight into the participants' satisfaction with the intervention programs and their components.

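### The mediation analysis keeps only mediators whose own arm effect reaches P<0.10, so a real mediator with a small effect can be left in the reported direct effect

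*Combined protocol and SAP*

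**What the plan says.** Section 12.4 (Mediation Analyses) sets out three steps.

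- **Entry condition:** "If the enhanced UC is more effective than UC for either primary outcome at 6 months, we will then conduct mediator analyses". Each primary outcome that is significant then gets its own mediation analysis.
- **Step 2:** each mediator's 2-month score is regressed on the intervention indicator. Only mediators with a P<0.10 "significant relationship with the intervention as potential mediators in the following step" go forward. Three candidates are named: self-efficacy, motivation and knowledge.
- **Step 3:** the probability of the assigned arm is modelled on the mediators, and the parenthesis defining that set reads "all mediators that were found associated with intervention in step 2". Inverse probability weights from this model are used in the outcome regression, and the weighted and unweighted arm effects are compared.

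The section says that this splits the total effect into an indirect effect through each mediator and a direct effect once all mediators are accounted for.

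**The concern.** Whether a mediator belongs in the decomposition is decided by a significance test in the data that are then decomposed. Missing P<0.10 is not evidence that a pathway is absent. If a real mediator misses it, the weights do not remove its contribution, and its path stays in what is reported as direct. A mediator that passes has been selected partly on a favourable chance deviation, so its step-2 coefficient, read after selection, is too large on average.

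The description of the direct effect does not match the procedure, which accounts only for the mediators that survive. The weighting as described in section 12.4 does not depend on a prior significance test. With three candidates named in advance and 718 participants in the primary analytic sample, there is no need to reduce their number.

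At stake is the reading of how the programme works: a direct effect that looks large could be partly an unrecorded pathway. Neither primary test is involved.

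**Working it through.** **1. The plan's own figures.** The documents give no power or error rate for the mediation steps. Their sample-size arithmetic can be checked to confirm the approximation. Section 12.2 powers the trial to "detect a 9% increase in abstinence rates between the UC (12%) and enhanced intervention (21%) at 6 months", "assuming a two-sided alpha-level=0.05 Wald Z test statistic for a difference between proportions using a normal approximation with pooled variance". Per arm:

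n = [1.960·√(2·p̄(1−p̄)) + 1.282·√(p₁(1−p₁) + p₂(1−p₂))]² / (p₂−p₁)²

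With p₁ = 0.12, p₂ = 0.21 and p̄ = 0.165, n = 355.4, rounded up to 356 per arm, or 712 in total, as stated. The other five rows of Table 2 also reproduce (880, 590, 856, 664, 376).

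**2. Inputs for the screen.**
- Primary analytic sample 718, about 359 per arm (section 12.4).
- Threshold P<0.10 (section 12.4). Sidedness is not stated; two-sided is assumed, so the critical value is 1.645.
- 2-month response: not given. Assumed 75-85%, so 359 × 0.75 = 269 to 359 × 0.85 = 305 per arm.
- True mediator effect d in SD units: not given. Shown for 0.10 to 0.30.

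**3. Chance of passing.** SE = √(2/n), which is 0.0862 SD at 269 and 0.0810 SD at 305. A mediator passes if its estimate exceeds 1.645 × SE in size, that is 0.142 or 0.133 SD.

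P(pass) = Φ(d/SE − 1.645) + Φ(−d/SE − 1.645)

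Example: d = 0.15, n = 269. d/SE = 1.740, so P = Φ(0.095) + Φ(−3.385) = 0.538.

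| True effect (SD) | Passes, 269 per arm | Passes, 305 per arm | Mean step-2 estimate when it passes ÷ truth |
|---|---|---|---|
| 0 | 10% | 10% | – |
| 0.10 | 32% | 34% | 1.9 |
| 0.15 | 54% | 58% | 1.4 |
| 0.20 | 75% | 80% | 1.1-1.2 |
| 0.25 | 90% | 93% | 1.0-1.1 |
| 0.30 | 97% | 98% | 1.0 |

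All three mediators survive at 0.15 SD in 0.538³ = 16% to 0.582³ = 20% of trials if they are independent; positive correlation raises this. At least one of three independent null mediators passes in 1 − 0.9³ = 27%.

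**4. Sensitivity.** The step-2 model lists only the intervention indicator as predictor. Adjusting for the baseline score (assumed correlation 0.5, 80% response) would raise the pass rates at 0.10, 0.15 and 0.20 SD from 33%, 56% and 77% to 40%, 67% and 87%.

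**5. Size of the shift into the direct effect.** This needs a mediator-to-outcome association, which the documents do not give. As an illustration, take the log-odds product: share = d × ln(OR per SD) / ln(OR total). At the design rates, ln(OR total) = ln[(0.21/0.79)/(0.12/0.88)] = 0.67. The expected shift is share × (1 − P(pass)).
- OR 1.5-2 per SD, d = 0.10: true share 6-10%, expected shift about 4-7% of the total effect per mediator.
- OR 1.5-2 per SD, d = 0.20: true share 12-21%, expected shift about 2.5-5%.
- OR 3 per SD, d = 0.10: true share 16%, expected shift about 11%.

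For uncorrelated mediators these add, so three come to at most three times these figures. Correlation with a retained mediator reduces them.

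**The case against.** The strongest defence is that the screen removes little that matters. A mediator likely to be dropped has a small arm effect, so it can usually carry only a small share of the total, as step 5 of the working shows. From 0.25 SD upwards it passes about nine times in ten or more. The overstatement when it passes concerns the step-2 coefficient, not the weighted-versus-unweighted contrast that the plan reports, and the secondary-outcome models in section 12.4 estimate arm effects on these measures without selection. All of this stands, and it limits the size of the problem. It does not justify the rule: where effects are large the filter does nothing, and where they are small it misplaces part of the pathway.

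A reader might infer two stronger things.

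- *That real mediators will usually be lost, or that most of the indirect effect will be relabelled as direct.* The documents give no mediator effect size to support this. For each of three mediators to carry 20% of the effect at 0.10 SD, each would need ln OR = 0.20 × 0.67/0.10 = 1.34, an odds ratio of about 3.8 per SD.
- *That the condition on a positive primary outcome leaves the objective in section 3.1, "or whether further refinement and evaluation are warranted", without an answer in a null trial.* Arm effects on secondary outcomes are estimated whatever the primary result, and the process and acceptability analyses also go ahead. Section 12.4 asks whether mediators explain part of an effect, which presupposes one, so this condition is a defensible choice.

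**Conclusion.** The point holds for the P<0.10 screen. The procedure does not deliver the direct effect that the section describes, and a real but small mediator has a substantial chance of being left out: about two in three at 0.10 SD, a little under one in two at 0.15 SD and one in four or five at 0.20 SD. At 0.25 SD or more the loss is minor. These figures rest on an assumed 75-85% response at 2 months, a two-sided test and no baseline adjustment. The effect on the direct/indirect split cannot be computed from the documents; under the illustrative odds ratios of 1.5-2 per SD it is modest for any one mediator. This is a low-cost improvement to a secondary analysis.

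The condition on a significant primary outcome deserves an optional note only. Where a primary outcome is not significant, the plan gives no mediator-to-outcome link and no indirect-effect estimate for it, even if the other outcome is positive. At 359 per arm and a 12% control rate, abstinence would miss significance in 10%, 20% or 52% of trials for a true gain of 9, 7.6 or 5 points.

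**What to change.** Change the mediation paragraph of section 12.4 as follows.

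- Name self-efficacy, motivation and knowledge as the fixed mediator set, and enter all three in the weighting model whatever their step-2 P values.
- Report the step-2 arm effects as estimates with confidence intervals, not as a filter.
- Report the direct effect and each indirect effect with bootstrap confidence intervals, re-estimating the weights in each resample.

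Optional: where a primary outcome is not significant, add the same analysis for it, labelled exploratory.

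The cost is a few sentences in the plan and some programming. Intervals will be slightly wider, because mediators with little arm effect stay in the model. The optional addition brings more exploratory results to report. No new data are needed, and the sample size and the primary tests are unchanged.

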7.3.2.5 Follow-up Assessments

Follow-up phone surveys will be conducted by the GHRI Survey Research Program at 2 and 6 months post-enrollment. Each participant will receive a reminder letter and text message approximately one week prior to their interview due date. Professional interviewers will then contact each person by phone to complete the standardized interview.

Persons who are reached by phone but who decline to participate in the full interview will be asked to provide information on each of the main outcomes of interest. Each

person who completes an interview (full or abbreviated) will be mailed a thank you letter and \$30 check or gift card as a thank you for their time.

During each follow-up contact, survey staff will confirm that the contact information on file is correct for each participant (mail address, cell phone number, home number, and email address).

Persons who cannot be reached within 2 weeks of their scheduled due date will be mailed a written survey to complete and return by mail. Persons who are not reached by phone and do not return the written survey within 4 weeks post-due date at 2 month follow-up or 6 weeks post-due date at 6 month follow-up will be coded as unable to reach. Other response options include: refused, deceased, and unknown.

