12.4 Final Analysis Plan

Analytic Samples. At the request of our DSMB, main outcomes will be analyzed using two analytic samples. One will include all 737 initially enrolled participants, regardless of study eligibility or study retention. Since no follow-up data is being collected on 19 of these individuals because they were ineligible and mistakenly enrolled, primary outcome data for these individuals will be treated as missing data. The second analytic sample (n = 718) will be limited to those individuals who were eligible to participate and included in the study. Analytic findings based on this second analytic sample will be considered the primary study results, but we will present the results from both analyses if results for the primary outcomes differ between the two samples. However, since missing data will be imputed as smokers and non-utilizers of dental care, and the 19 individuals not included in the primary analytic sample were equitably distributed across groups (9 vs. 10), we do not anticipate their exclusion will alter the primary findings. All analyses will use an ITT methodology such that subjects are analyzed according to their assigned treatment group, regardless of noncompliance, protocol deviation or withdrawal from treatment utilization.

Primary and secondary analyses. To assess the difference between the experimental and control groups for smoking abstinence, the regression model will include data from both follow-up time points in a single model to improve power and adjust for possible correlation within

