individuals using generalized estimating equations.¹ To assess differences in dental care utilization, we will compute whether participants saw a dentist post-enrollment using data from each follow-up, then run a single logistic regression model. We will specify an independent working correlation structure and estimate robust standard errors to avoid making model assumptions about the variance. Models will use a logit link function for the binary primary outcomes and odds ratios will be used to quantify differences between groups. To improve precision and power, analyses will be adjusted for the following pre-specified baseline characteristics that are expected, based on prior knowledge, to be important predictors of outcome or missing data: sex, age, pharmacotherapy use (e.g., NRT), baseline cigarettes per day, depression history, self-efficacy, and motivation for quitting. Models will also adjust for variables used to stratify randomization (dental insurance coverage and state quitline).

To estimate the effects of the intervention on secondary outcomes (e.g., completing or scheduling a dental appointment, brushing, self-efficacy, motivation, etc.), we will apply similar regression models as described for the primary outcomes, using appropriate link functions dependent on outcome type, and further adjust for baseline outcome value when appropriate.

To handle missing follow-up data for the primary outcomes we will assume that missing subjects are smokers and are non-users of dental service. In sensitivity analyses, we will use modern imputation methods to impute missing outcome data, based on the observed pattern of missingness.² We also will conduct a respondent only missing data sensitivity analysis that only includes subjects with observed outcome data (i.e., a complete case analysis).

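### The mediation analysis inherits the missing = smoker rule with no sensitivity check and no rule for missing 2-month scores, so a score that only predicts answering the 6-month survey can appear to mediate abstinence.

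*Combined protocol and SAP*

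**What the plan says.** Section 12.4 (Mediation Analyses) runs mediation only if the enhanced programme is more effective on a primary outcome, and only for 2-month scores (self-efficacy, motivation, knowledge) that differ by arm at P < 0.10. It fits a logistic model for arm given the mediators and baseline confounders: "From this model we will obtain the estimated probabilities that each person received their observed intervention given their observed mediator value". An inverse-probability-weighted regression of the primary outcomes on arm follows. The share explained comes from comparing the weighted with the unweighted model. No test or interval is named for that share.

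The outcome rule is set earlier in 12.4 and in 3.2.1: "To handle missing follow-up data for the primary outcomes we will assume that missing subjects are smokers and are non-users of dental service". Section 12.4 adds an imputation analysis and a respondent-only analysis as sensitivity analyses for missing outcome data. The mediation text refers to neither.

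Section 7.3.2.5 describes three routes to incomplete 2-month data. Some people are never reached. Some may answer only a mailed survey, whose content is not in the text reviewed. Those who "decline to participate in the full interview will be asked to provide information on each of the main outcomes of interest" may give no mediator items. The plan does not say how a missing mediator score is handled or who forms the mediation sample. For the main outcomes, by contrast, it defines the samples explicitly ("The second analytic sample (n = 718) will be limited to those individuals who were eligible").

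**The concern.** Under missing = smoker, the analysed outcome is a product: abstinent and answered. Anything that predicts answering therefore also predicts the analysed outcome. If the programme raises motivation at 2 months, and motivated people are more likely to take the 6-month call, weighting out motivation removes an arm difference in response. The plan would count that as mediation of abstinence.

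The link is plausible. Section 12.4 lists baseline self-efficacy and motivation for quitting among covariates chosen because they are expected to predict outcome or missing data. The same constructs, measured at 2 months, are candidate mediators.

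Mediation is a stated hypothesis (12.1) and part of a secondary objective (3.1). The result would inform how the programme is understood and refined. Section 3.2.2 plans to check whether imputation matters for abstinence itself, but mediation gets no such check.

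**Working it through.** **The plan's own figure.** Section 12.2 gives no number for mediation, but its abstinence rates are inputs here, so its sample size was checked first. The inputs are "9% increase in abstinence rates between the UC (12%) and enhanced intervention (21%) at 6 months", "assuming a two-sided alpha-level=0.05 Wald Z test statistic for a difference between proportions" and "All power calculations assume 90% power and use a normal approximation approach with pooled variance".

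n per arm = [1.960·√(2 × 0.165 × 0.835) + 1.282·√(0.12 × 0.88 + 0.21 × 0.79)]² / 0.09² = (1.029 + 0.668)² / 0.0081 ≈ 355.4. That rounds up to 356 per arm, 712 in total, as stated. All six rows of Table 2 reproduce.

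**Set-up for the mediation check (assumptions, not in the documents).**
- Arms are 1:1. The mediator M is standard normal in usual care and shifted by d = 0.2–0.5 SD in the enhanced arm.
- The probability of answering at 6 months, r(M), is logistic in M, with odds ratio 1.5–2.0 per SD and a fixed overall mean.
- True abstinence is 0.12/0.7 = 17.1% against 0.21/0.7 = 30%, independent of M and of response. At 70% response the analysed rates are then about 12% and 21%.
- There is no true mediation.

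**Formulae.**
- Unweighted analysed rate in arm a = true rate × mean of r(M) in that arm.
- Weights of 0.5/P(arm | M) give both arms the same mediator distribution, so weighted rate = true rate × overall response.
- False share = 1 − weighted log OR / unweighted log OR.

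**Worked case: 70% response, OR 2.0, d = 0.5.**
- Response is 66.7% in usual care and 73.3% in the enhanced arm.
- Unweighted rates: 0.1714 × 0.667 = 11.4% and 0.300 × 0.733 = 22.0%. Log OR = −1.266 + 2.047 = 0.781.
- Weighted rates: 12% and 21%. Log OR = −1.325 + 1.992 = 0.668.
- False share = 1 − 0.668/0.781, about 14.6% before rounding.

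**Full range (numerical integration).**

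| 6-month response | OR 1.5, d = 0.2 | OR 2.0, d = 0.5 |
|---|---|---|
| 90% | 1.4% | 5.6% |
| 80% | 2.8% | 10.4% |
| 70% | 4.1% | 14.6% |
| 60% | 5.3% | 18.4% |

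At OR 1.0 the share is zero. Simulations of this model agree to within about a point.

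**Closer to the plan.** A simulation also adjusted for the baseline mediator, with 75% assumed to have a 2-month score, 70% six-month response and d = 0.2–0.6. It gave false shares of 1.7–5.2% at OR 1.25, 3.0–8.7% at 1.5, 5.2–14.0% at 2 and 7.3–19.5% at 3. Among 6-month respondents only, the share was −0.6% to 0.3% throughout, which isolates missing = smoker as the cause.

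**At n = 718, among trials passing both entry conditions.** A mediator with no effect on abstinence was significantly and positively related to the analysed outcome in 2–3% of trials at OR 1, 13–15% at OR 1.5 and 23–28% at OR 2. Among respondents the figure was 1–3%. The entry conditions do not remove the artefact.

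**Dental care (about 5% vs 15%, d = 0.4–0.6, OR 1.5–2).** The false share is 3.3–7.6% if no visits fall before month 2, 1.7–5.0% if a third do, and 0.9–2.7% if two thirds do.

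**Precision.** If 10–40% lacked a 2-month score and were dropped (assumed), the sample would fall from 718 to about 646–431. Standard errors would rise by √(718/646) = 1.05 to √(718/431) = 1.29, that is by 5–29%.

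**The case against.** A reader might infer more than the documents support, on five counts.

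- *That false mediation will be reported.* It requires a primary effect, an arm difference in the mediator at P < 0.10, and a mediator that predicts 6-month response. The plan also calls this work exploration. The result is possible, not certain.
- *That every 6-month non-responder is a dental failure.* Sections 3.2.1 and 12.4 use reports from either follow-up, so a visit reported at 2 months counts whatever happens at month 6. The dental artefact is smaller for that reason.
- *That a total effect in 718 people is compared with a direct effect in a subset.* Section 12.4 compares weighted with unweighted models and does not say they use different people. The first-step total effect does come from the full sample, so this is an ambiguity to close and not an error.
- *That people giving the short interview cannot be scored.* Section 7.3.2.5 does not say they are asked only the main outcomes, and the mailed survey is another possible source. What stands is that no rule is given.
- *That imputation must become the main mediation analysis.* The effect that opens the mediation step is itself defined with missing = smoker, so decomposing that effect is defensible. Replacing it is a matter of judgement.

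Size is also a fair objection. People with a 2-month score have already responded once, and incentives, mail follow-up and abbreviated interviews are planned, so their 6-month response may be high. At 85% response the false share is about 2.1–7.9%, and at 95% about 0.7–3.0%. With no artefact, the estimated share at n = 718 and 80% response already has a sampling SD of about 3–8 points. At high response the bias is therefore no larger than noise. That limits the importance of the point but does not remove the gap.

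**Conclusion.** The point holds in limited form. The mediation plan applies missing = smoker/non-user through its outcome definition, is silent on missing 2-month scores, and has no sensitivity analysis of its own. For abstinence, a score that predicts only survey response can then be credited with mediation, by the amounts tabulated above. Those figures rest on assumed response rates, response odds ratios and mediator shifts, and on abstinence being unrelated to response. They vanish if the score does not predict response. The matter merits a change because following the stated outcome rule can itself produce the artefact, and the plan already has the tools to expose it. It does not touch the primary analyses, the primary conclusions or the sample size.

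**What to change.** In section 12.4, Mediation Analyses:

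1. State that missing 2-month mediator scores will be multiply imputed, using arm, baseline covariates and the other follow-up data.
2. State that the unweighted and weighted models are fitted in the same people.
3. Repeat the mediation analysis with the imputed and the respondent-only 6-month outcomes already planned as sensitivity analyses. Report these beside the missing = failure version, and do not claim mediation that appears only under missing = failure.

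The cost is a paragraph of text, modest extra programming, and a footnote explaining that the total effect differs between versions. No new data are needed.
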